10.4.1. Exploratory subgroup analyses

The proportion of subjects who respond to treatment (achieve at least a 50% reduction from baseline in the number of UUI episodes per 24 hours on a 3-day voiding diary after 48 weeks of eCoin™ tibial nerve stimulation) will be summarized for various subgroup populations based on baseline characteristics, demographics, and effectiveness endpoints. For each subgroup, a forest plot will show the proportion of responders along with its 95% confidence interval. A logistic regression may also be used to describe the relationship between response to treatment and different subgroup populations.

10.4.2. Additional OAB medications

Medications for OAB are not allowed until the primary effectiveness endpoint is reached at 48 weeks post-activation, unless judged medically necessary. Any subjects who have taken OAB medications will be included in the primary effectiveness outcome variable analysis. OAB medication use will be reported alongside the primary analysis. The timing of OAB medications will be displayed, including duration of treatment, start and end dates, and dosage.

The following additional sensitivity analyses may be performed.

- For the primary effectiveness outcome variable at week 48, data for subjects who have taken OAB medications while on study will be considered missing and imputed assuming they had not taken any OAB medication.
- For weeks 4, 8, 12, 24, 36, and 48, 2 different sets of analyses will be performed.
 - *While on OAB medication.* Subjects will be imputed as non-responders while they are taking OAB medication.
 - *Any OAB medication.* A very conservative set of analyses will consider a subject a non-responder at every visit after she starts OAB medication.

For example, no matter what subjects write on their diaries, the “while on OAB medication” analyses will consider subjects as non-responders from week 12 through week 36 if they take OAB medication at week 12 and stop that medication at week 36. The “any OAB medication” analyses will consider such subjects non-responders from week 12 through week 48.

11. Safety summaries

11.1. Adverse events

Adverse events (AEs) will be continuously monitored throughout the study. Investigators will classify each AE according to its relationship to study device (certainly, probably, possibly, unlikely, not related, or unclassified), intensity (mild, moderate, or severe), and seriousness. AEs will be coded using version 20.0 or later of the MedDRA dictionary and summarized by system organ class (SOC) and preferred term (PT). AEs will be summarized by subject, not event. All summaries will include the number of subjects who undergo a procedure for implantation of eCoin™ and the number of subjects with at least one event.

All AE presentations will summarize treatment-emergent adverse events (TEAEs), defined as AEs with onset on or after the device implantation procedure. AEs with completely missing onset date will be assumed treatment-emergent events. The ITT population will be used for all AE analyses.

The following presentations of treatment-emergent adverse events will be generated:

- All adverse events
- All adverse events related to study device (i.e., AEs classified as certainly, probably, and possibly related)
- All adverse events related to study device up to 52 weeks after implantation (the primary safety outcome)
- All adverse events related to study device up to 28 weeks after implantation (the secondary safety outcome)
- All adverse events related to study procedure
- Serious adverse events, and
- Adverse events leading to study discontinuation.

All AEs will be presented in a listing with SOC, PT, onset and resolution dates, study day relative to implantation, study day relative to device activation, seriousness, relationship to study device, relationship to study procedure, actions taken with study device, and outcome.

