- Subjects for whom 48 week post-activation data are unavailable but the device is known not to have been explanted will have their missing data imputed. The missing data for the primary effectiveness outcome variable will be assumed missing at random and will be handled with multiple imputation.
- Any subject who undergoes the procedure for implantation of eCoin[™] whether or not the device is actually activated, will be treated as if they were activated.
- An addendum to the SAP addresses missing data related to COVID-19 impact.

Multiple imputation will be performed under fully conditional specification (FCS) with 100 imputed datasets. The model will include the following variables: sex, age, body mass index (BMI), response to the TENS protocol, OABq total score at baseline and all follow-up visits, Patient Global Impression of Improvement questionnaire score at all post-baseline visits, average urinary voids per 24 hours on a 3-day voiding diary at baseline and all follow-up visits, and average UUI episodes per 24 hours on a 3-day voiding diary at baseline and all subsequent visits. The SAP will contain further details and SAS code concerning the modelling for multiple imputation.

The SAP will provide further details on handling missing data for the secondary outcomes. For the analysis of safety variables, only partial dates may be imputed; otherwise, missing data will be treated simply as missing. Conventions for imputing partial dates will be described in the SAP.

Pivotal Study of Subcutaneous Tibial Nerve Stimulation with eCoin[®] for Urgency Urinary Incontinence.

3-9-7 Sensitivity and additional analyses

The primary and secondary efficacy analyses will be repeated for all analysis populations (mITT, OAB drug-free, Per-protocol, Responders, and TENS cohort analysis). These analyses will also be repeated for the mITT analysis population excluding any subjects enrolled but not meeting all eligibility criteria who were subsequently re-baselined to correct any eligibility violations.

Additional sensitivity analyses may be conducted to evaluate different methods of handling missing data, such as tipping point, best-case, and worst-case scenario analyses. Additional sensitivity analyses are described in the SAP addressing COVID-19 impact.

3-9-7-1 Additional OAB medications

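### SAP 11.1 has no rule for adverse events left 'unclassified' for relationship to the device, so the primary safety outcome may be understated

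*SAP*

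**What the plan says.** SAP 11.1 has investigators rate each event's "relationship to study device (certainly, probably, possibly, unlikely, not related, or unclassified"). The table of device-related events is specified as "All adverse events related to study device (i.e., AEs classified as certainly, probably, and possibly related"). The primary safety outcome is the same table restricted to one year: "All adverse events related to study device up to 52 weeks after implantation (the primary safety outcome"). A 28-week version is the key secondary safety outcome. Counting is by subject ("AEs will be summarized by subject, not event"), the population is ITT, and every summary shows the number of subjects who underwent the implantation procedure.

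The section deals with one other unknown: "AEs with completely missing onset date will be assumed treatment-emergent events". It says nothing about querying, adjudicating or assigning an unclassified relationship.

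The protocol works differently. Section 3-8-6-3-1 has a two-level scale, related or not related, with no third value. Section 3-8-6-4 has a medical reviewer, on or designated by the DSMB, assign relatedness for every adverse event. Section 3-9-6 adds: "For the analysis of safety variables, only partial dates may be imputed; otherwise, missing data will be treated simply as missing".

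**The concern.** *Unclassified* means that no judgement on causality was reached. In the device-related tables the SAP gives it the same consequence as a judgement against causality. The subject stays in the denominator, because all implanted subjects are there, and adds nothing to the numerator.

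The study is a single-arm pivotal trial meant to support a pre-market approval application. There is no comparator in which a similar under-count would occur, so the reported device-related rate is itself the safety evidence. The 52-week table as described does not ask for the number of unclassified events, so its reader would not see how many had been left out.

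**Working it through.** The plan states no expected device-related rate, safety margin or safety sample size, so there is no safety figure to reproduce. The check has two parts.

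**1. Where does an unclassified event go?** Each SAP relationship level is set against the definitions.

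| SAP level | In the SAP device-related tables? | Protocol 3-8-6-3-1 |
|---|---|---|
| certainly, probably, possibly | yes | no mapping given |
| unlikely, not related | no | no mapping given |
| unclassified | no | no such level |

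The protocol's *not related* needs a positive finding: the event is independent of the therapy, or another cause appears to explain it. An unclassified event has no such finding, yet it falls on the same side of the SAP table. It does still appear in the all-event table, in the serious and discontinuation tables where it qualifies, and in the listing: "All AEs will be presented in a listing with SOC, PT, onset and resolution dates, study day relative to implantation", with relationship to the device among the later fields.

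**2. How much could this matter?** Inputs:

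- N = 120 (target) or 135 (maximum), from SAP 2.1.
- x = subjects with at least one event rated certainly, probably or possibly related within the window. Not in the documents; assumed to be 12 or 24.
- u = subjects whose only candidate related event in the window is unclassified. Not in the documents; assumed range 0 to 12.

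As the SAP is written, the proportion is x/N. With unclassified counted as related it is (x + u)/N. The difference is u/N, which is never negative and is zero when u = 0. Per affected subject it is 1/120 = 0.83 points, or 1/135 = 0.74 points.

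Proportions with exact (Clopper-Pearson) 95% intervals. The u = 0 row is the SAP result.

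| u | x = 12, N = 120 | x = 24, N = 120 | x = 12, N = 135 |
|---|---|---|---|
| 0 | 10.0% (5.3 to 16.8) | 20.0% (13.3 to 28.3) | 8.9% (4.7 to 15.0) |
| 1 | 10.8% (5.9 to 17.8) | 20.8% (14.0 to 29.2) | 9.6% (5.2 to 15.9) |
| 3 | 12.5% (7.2 to 19.8) | 22.5% (15.4 to 31.0) | 11.1% (6.4 to 17.7) |
| 6 | 15.0% (9.1 to 22.7) | 25.0% (17.5 to 33.7) | 13.3% (8.1 to 20.3) |
| 12 | 20.0% (13.3 to 28.3) | 30.0% (22.0 to 39.0) | 17.8% (11.7 to 25.3) |

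The intervals only give scale; the plan specifies no confidence interval for safety. A subject who also has a related event in the window is already counted in x, so only a preferred-term row could change for that subject.

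**The case against.** A reader might infer that the SAP declares unclassified events not device-related and that the primary safety outcome is therefore biased downward. The documents do not support that. No sentence labels these events not related, and they remain visible in the all-event table and the listing. Understatement needs three things: unclassified events remaining at lock, some of them truly device-related, and, for the overall subject count, no other related event in that subject's window. The documents establish none of the three.

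The protocol's process could also empty the category. The reviewer assigns relatedness to every event, causality is a field on the event form, the principal investigator or sub-investigator must sign the assessment, and the protocol scale has only two values. This is the strongest counter-argument, and it stands as a reason why the number may be zero. It does not close the gap. SAP 11.1 refers only to investigators, permits *unclassified* without requiring its resolution, and does not say whose assessment drives the table. The SAP also claims precedence over the protocol on minor differences.

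A reader might also treat the missing-onset-date rule as the SAP's own precedent for conservative counting. It is a weak one. That rule makes an event treatment-emergent, but SAP 13.1 does not impute completely missing dates, so the rule alone does not place the event within 28 or 52 weeks. In addition, *unclassified* is a recorded value rather than an absent one.

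Two further points stand. Safety is a descriptive tabulation with no hypothesis or performance goal, so no formal decision changes. And counting a missing relationship as related conflicts with the protocol's sentence in 3-9-6, so the two must be reconciled.

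**Conclusion.** The gap is real and its direction is known. As SAP 11.1 is written, an event still unclassified at lock is handled in the device-related tables like an *unlikely* or *not related* one. This can lower the 28-week and 52-week subject counts or leave them unchanged, but cannot raise them. The size is 0.83 points per affected subject at 120 and 0.74 at 135. The number of affected subjects is not in the documents and may be zero, so the conclusion is that the primary safety outcome may be understated, not that it is. The exclusion follows from the SAP's own definition, so it is a stated rule and not merely missing detail. It is worth correcting because the related-event rate is the primary safety result of an uncontrolled study and the correction is cheap.

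**What to change.** In SAP 11.1:

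- Require every unclassified or missing relationship to be resolved before database lock through the medical-reviewer assignment in protocol 3-8-6-4. Say whose assessment governs the tables and how the six SAP levels map to the protocol's two.
- Count any event that remains unclassified or without a relationship as device-related in the all-time, 28-week and 52-week related tables. Footnote the number of subjects included only for that reason, so that a reader can recover the narrower count.
- Reconcile this with protocol 3-9-6, for example by stating that the counting rule is a tabulation convention that applies despite the sentence treating missing safety data as missing.

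The cost is a few sentences, a footnote, and the work of clearing open relationship fields before lock. The downside is that the reported related-event rate may be slightly higher, and somewhat overstated if the remaining events were in truth unrelated; the footnote shows by how much at most. If none remain, the tables do not change.

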3-8-6 Safety and Adverse Events

3-8-6-1 Medical Monitoring

The study will be approved by a study-wide independent ethical committee or institutional review board. The participating Investigators will monitor the subjects medically.

3-8-6-2 Definitions of Adverse Events

Adverse Event (AE): Any untoward medical occurrence in a study participant whether or not there may be a causal relationship with this treatment / intervention. This can include (but is not limited to) worsening of subject's overactive bladder condition and/or occurrence of serious sudden events.

System and Procedure Related Adverse Event: Any adverse event related to the device or placement procedure. This can include risks associated with the procedure, implant site or stimulation such as infection, or unexpected related adverse events that occur in relation to implant placement, tibial nerve stimulation or device failure. The Sponsor maintains a list of expected adverse events and is responsible for determining expectedness.

3-8-6-3 Classification of Events

3-8-6-3-1 Relationship

YES- related: The event has a reasonable possibility of a causal relationship to the administration of tibial nerve stimulation (procedure, device, or stimulation) and no other etiology explains the event.

NO- not related: The event is independent of tibial nerve stimulation (procedure, device, or stimulation) and/or the event appears to be explained by another etiology.

3-8-6-3-2 Severity

Mild: Transient or mild discomfort (<48 hours); no medical intervention/therapy required and does not interfere with the subject's daily activities.

Moderate: Some limitation in activity; some assistance may be needed; no or minimal medical intervention/therapy required.

Severe: Marked limitation in activity; interrupts participant's usual daily activity and may require medical intervention/therapy; hospitalization possible.

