Serious: Results in death during the study period; is life-threatening; requires hospitalization or prolongation of existing hospitalization; results in persistent or significant disability or incapacity; results in a congenital anomaly or birth defect; requires medical or surgical intervention to preclude permanent impairment of a body function or to prevent permanent damage to a body structure, where the device is suspected to cause such intervention; other important medical events not captured by the other categories where the event may jeopardize the patient and may require medical or surgical intervention to prevent one of the other outcomes.

3-8-6-3-3 Expectedness

Expected: Any adverse reaction whose nature and intensity are consistent with that described under risk assessment.

Pivotal Study of Subcutaneous Tibial Nerve Stimulation with eCoin[®] for Urgency Urinary Incontinence.

Unexpected: Any adverse reaction not included under risk assessment.

3-8-6-4 Recording of Adverse Events

Expected device-related AEs will be recorded on case report forms as shown in Attachment 4-9, which are used at each visit. Unexpected or unrelated AEs or any requiring medical attention will be reported on CRFs and further recorded on AE forms. Subjects will be requested to report adverse urologic events that are inconsistent with their normal medical condition that occur in between visits to the study coordinator or medical staff who will record on AE forms. All adverse events will need to be evaluated and assigned by a medical reviewer on or designated by the Data and Safety Monitoring Board (DSMB) with regards to:

- 1) Relatedness or causality to the study device
- 2) Severity
- 3) Expectedness
- 4) Action taken

The Sponsor is responsible for determining if an adverse event is unexpected. If expectedness is assessed by a medical reviewer as unexpected, the Sponsor will be notified and will evaluate and assign a final determination that may or may not result in a requirement to report expeditiously to regulators, IRBs, or both.

At each contact with the subject, the Investigator will obtain information on AEs by specific questioning and examination. In the CRF for visits, if an event is reported, the AE checkbox will be selected. This selection will trigger a separate form to be filled out that records the following information:

1. Subject Number
2. Adverse Event (AE)
3. Date of AE onset
4. Date of AE cessation
5. Severity
6. Expectedness
7. Causality

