- 1) AEs that are device-related resulting in a revision surgery or explant (explant for reasons other than for normal end of life – e.g. battery depletion) for which the patient presents to the PI.
- 2) AEs that occur during or related to an explant procedure performed at the normal device end of life.

3-8-7 Subject Withdrawal & Termination

This section describes reasons for withdrawal of subjects and termination of the study. A Statistical Analysis Plan (SAP) will describe in detail the methods for handling data from subjects who withdraw, or are withdrawn, early from the study.

3-8-7-1 Early Withdrawal of Subjects

Subjects may voluntarily withdraw from the study for any reason at any time. They may be considered withdrawn if they state an intention to withdraw, fail to return for visits, or become lost to follow-up for any reason. The devices must be recommended to be explanted if the subject is withdrawn.

3-8-7-2 Terminating Subject Participation

A subject's continued participation in the study must be terminated if in the Investigator's opinion, continued participation would be detrimental to the subject's well-being. If the subject is unwilling or unable to attend all remaining follow-up visits, or if subject is lost to follow-up, the subject's continued participation must be terminated. If the subject is explanted for any reason, subject participation must be terminated.

The subject's eCoin[™] system must be recommended to be explanted if the subject's participation is terminated.

3-8-7-3 Withdrawal/Termination Procedures

If premature withdrawal occurs for any reason, the Investigator must make every effort to determine the primary reason for a subject's premature withdrawal from the study and record this information on the Case Report Form for reporting to the Sponsor.

Pivotal Study of Subcutaneous Tibial Nerve Stimulation with eCoin[®] for Urgency Urinary Incontinence.

Subjects enrolled in the study will not be replaced if they withdraw or are terminated from the study after device activation. Provisions for device explantation will be arranged.

3-8-7-4 Early Study Termination

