The primary effectiveness outcome is achieving at least a 50% reduction from baseline in the number of urgency urinary incontinence episodes per 24 hours on a 3 day voiding diary after 48 weeks of eCoin[™] tibial nerve stimulation.

The proportion of responders along with its 2-sided 95% exact Clopper-Pearson confidence interval will be summarized after 48 weeks of therapy.

3-9-3-3-2 Key Secondary Effectiveness Outcome

The key secondary effectiveness outcome is achieving at least a 50% reduction from baseline in the number of urgency urinary incontinence episodes per 24 hours on a 3 day voiding diary after 24 weeks of eCoin[™] tibial nerve stimulation.

Pivotal Study of Subcutaneous Tibial Nerve Stimulation with eCoin[®] for Urgency Urinary Incontinence.

The proportion of subjects with at least 50% reduction from baseline along with its 2-sided 95% exact Clopper-Pearson confidence interval will be summarized after 24 weeks of therapy.

3-9-3-3-3 Primary Safety Outcome

The primary safety outcome is device-related adverse events from implantation to 52 weeks after implantation of eCoin[™].

All device-related adverse events up to 52 weeks after implantation of eCoin[™] will be summarized by preferred term. Tabulations of these data will include the number of subjects exposed and the number of subjects with at least one device-related adverse event.

3-9-3-3-4 Key Secondary Safety Outcome

The key secondary safety outcome is device-related adverse events 28 weeks after implantation of eCoin[™].

All device-related adverse events up to 28 weeks after implantation of eCoin[™] will be summarized by preferred term. Tabulations of these data will include the number of subjects exposed and the number of subjects with at least one device-related adverse event.

3-9-3-3-5 Secondary Outcomes

The secondary outcomes listed in this section are based on data after 24 and 48 weeks from activation (28 and 52 weeks after implantation). These outcomes, which are for descriptive purposes, will not be formally analyzed statistically. The SAP will describe in detail analyses of the secondary outcomes.

- Achieving 75% improvement in the number of urgency urinary incontinence episodes per 24 hours on a 3 day voiding diary.
- Achieving 100% improvement in urgency urinary incontinence episodes (“Dryness”) per 24 hours on a 3 day voiding diary.
- Reduction from baseline in the number of urgency urinary incontinence episodes per 24 hours on a 3 day voiding diary.

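### The protocol and SAP define a related adverse event differently for the 28- and 52-week safety outcomes, and SAP 11.1 plans no combined device-or-procedure subject count at either time

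*SAP*

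**What the plan says.** Protocol 3-9-3-3-3 sets the outcome: "The primary safety outcome is device-related adverse events from implantation to 52 weeks after implantation". Section 3-9-3-3-4 does the same at 28 weeks. Both ask for the number of subjects with at least one such event. Neither says whether events caused by the implant procedure count.

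On relatedness, protocol 3-8-6-3-1 offers only yes or no. Yes means: "The event has a reasonable possibility of a causal relationship to the administration of tibial nerve stimulation (procedure, device, or stimulation", and also that no other cause explains the event. Section 3-8-6-4 adds a reviewer: "All adverse events will need to be evaluated and assigned by a medical reviewer on or designated by the Data and Safety Monitoring Board". The first attribute on that reviewer's list is "Relatedness or causality to the study device". The same section lists a single causality item among the form fields and requires the PI or sub-PI to sign the assessment.

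SAP 11.1 reads: "Investigators will classify each AE according to its relationship to study device (certainly, probably, possibly, unlikely, not related, or unclassified". Certainly, probably and possibly count as related. The SAP plans device-related tables uncut, to 52 weeks and to 28 weeks, plus a table of events related to study procedure with no time cut. It describes the 52-week table as "All adverse events related to study device up to 52 weeks after implantation (the primary safety outcome". Counts are of subjects, not events. The listing carries relationship to device and relationship to procedure as separate columns.

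Protocol 3-9-8 also plans subject tabulations by time point, repeated for events causally related to the eCoin system, and tabulations of local AEs at 28 and 52 weeks after implantation. SAP 11.1 contains neither.

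**The concern.** These ratings decide which events enter the primary and key secondary safety outcomes. Two analysts, one working from the protocol and one from the SAP, could report different subject counts under the same outcome name.

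The boundary lies where events are expected. The safety window opens at implantation, about four weeks before activation. Protocol 3-6 names infection as the main safety concern, and 3-7-4-3 lists bruising, redness and incisional pain among the most probable risks of implantation. A rater could reasonably attribute such events to the surgery and not to the device. In a single-arm pivotal study of an implant, a reader will want the share of subjects with any device- or procedure-related event by each time point. The planned SAP tables do not give it.

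**Working it through.** There is no stated figure to reproduce, because the safety outcomes are descriptive. The check is a comparison of texts followed by a bound.

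**1. How each definition treats the same event**

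- Attributed to device or stimulation, no other cause: related in the protocol; in the SAP device count.
- Attributed to the procedure only, no other cause: related in the protocol; not in the SAP device count.
- Possibly due to the device, but another cause explains it: not related in the protocol; in the SAP device count.
- Left unclassified against the device: could be related in the protocol; not in the SAP device count.

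The second and fourth cases make the SAP count smaller, and the third makes it larger. The net direction cannot be read from the documents.

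**2. Whether the SAP tables can be combined**

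Let D be the subjects in the 52-week device table, P the subjects in the uncut procedure table, and N the ITT population. A subject may be in both tables. The number of procedure-table subjects whose event fell within 52 weeks can be anything from 0 to P. So the number U with either kind of event by 52 weeks satisfies

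D ≤ U ≤ D + P (and U ≤ N),

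and the combined rate is undetermined by up to P/N. The same holds at 28 weeks with that table's D. The documents give no D or P for this trial. With assumed counts at N = 120:

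- D = P = 5: U from 5 to 10, or 4.2% to 8.3%.
- D = P = 10: U from 10 to 20, or 8.3% to 16.7%.
- D = P = 20: U from 20 to 40, or 16.7% to 33.3%.

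These only show how the bound works. They are not estimates.

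**3. What the uncut procedure table may contain**

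The term study procedure is not limited to the implant. From the windows in protocol 3-4-2 (activation 23 to 43 days after implant, Visit 11 at 331 to 341 days after activation, explant 0 to 15 days after Visit 11), explant falls

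- earliest: 23 + 331 + 0 = 354 days after implantation, or 28 + 331 = 359 if the four-week healing minimum in 3-4-8 is applied;
- latest: 43 + 341 + 15 = 399 days.

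The 52-week cut is 52 × 7 = 364 days, which lies inside that range. Explant is later for extension subjects and may be later where COVID-19 delayed it (3-8-8). Whether those events enter the table depends on the data lock.

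**4. Whether the precedence rule settles it**

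Protocol 3-9-3 and SAP section 1 let the SAP prevail for minor differences in analyses. That supports using the SAP tables. It does not say how a yes/no record becomes one of six levels, or whether procedure events belong in the outcome.

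**The case against.** The strongest reply is that a literal device-only reading matches the outcome's name. Protocol 3-8-6-6 itself separates "AEs that are device-related resulting in a revision surgery or explant" from "AEs that occur during or related to an explant procedure performed at the normal device end of life", so the protocol can tell device events from procedure events. This stands: the SAP's device-only count is not an error.

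The difference in raters is also softer than it looks. The protocol has the PI or sub-PI sign the assessment as well as a DSMB-designated reviewer evaluate it, and SAP 11.1 plainly uses the investigator's classification. What remains is that no text says which rating prevails if the two disagree.

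A reader might infer that the SAP gives no safety counts at 28 or 52 weeks. It does: device-related subject counts are planned at both. A reader might also infer that procedure events are lost. They are not. They appear in the all-AE table, the procedure table and the listing, and incision symptoms are summarised by visit (SAP 11.2).

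Nor can it be said that only the listing could yield a combined count. If the causally related tables in protocol 3-9-8 use the protocol's yes/no rating, they already count device or procedure together. But 3-9-8 does not name their time points, the term local is undefined, and SAP 11.1 takes up neither set of tables.

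**Conclusion.** The point holds as a mismatch in definition plus a gap in the SAP tables, and it is worth fixing before database lock. Scope, scale and threshold differ between the documents for the primary and key secondary safety outcomes. A procedure-only event is related under one and uncounted under the other. SAP 11.1 has no procedure count at 28 or 52 weeks, no combined count, and no equivalent of the protocol 3-9-8 tables.

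The size is unknown: up to P/N for the combined rate, with P not given. A reader might infer that the SAP wording flatters the device. The documents do not support that, because counting possibly related events works in the other direction. A reader might also try to size the gap from incision-site events in the sponsor's hypertension study. That report does not split events into device and procedure, and it concerned two devices per subject at another nerve.

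The outcome is descriptive, so no success decision changes. The conclusion rests on the supplied text: the AE form and DSMB charter are not included. The SAP states that it is based on protocol version 3.6 of August 2019, while the supplied protocol, with its COVID-19 provisions, is evidently later.

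**What to change.** - Keep the device-related tables in SAP 11.1 as they are.
- Add subject counts for procedure-related events and for device-or-procedure-related events at the same 28- and 52-week cuts. Count each subject once in the combined row, and show implant and explant events separately.
- Align SAP 11.1 with protocol 3-9-8: either carry over the causally related and local-AE tables, with time points and a definition of local, or say that they are replaced.
- State once, in the same words in both documents, whether device-related includes procedure events, which rating is analysed (investigator or DSMB-designated reviewer), and how unclassified is handled.
- If the AE form collected only the protocol's yes/no rating, report that as a combined count and label it so. No mapping rule can split a combined yes into device and procedure.

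The cost is a little table programming, provided the form holds both relationship fields as the SAP listing implies, and a combined rate that may look less favourable than the device-only rate. Under SAP 7.3 these additions belong in a revised SAP before database lock; made later, they would be labelled exploratory. Widening the outcome itself, as opposed to stating its scope, could need a protocol amendment under 3-9-3.
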